ANNEX 3. LIST OF DIAGNOSIS CODES FOR SELECT INFECTIONS OF INTEREST

All codes will be reviewed and updated prior to study initiation. For a list of codes, see the following files:

- Final_A3921321_Xeljanz-EU DUS opportunistic infections Dx codes_v1.2.pdf
- Final_A3921321_Xeljanz-EU DUS serious infections DX codes_v1.2.pdf

ANNEX 4. LIST OF ATC CODES FOR COMEDICATIONS OF INTEREST

All codes will be reviewed and updated prior to study initiation.

Class of drug	Drug	ATC code
Corticosteroids	Aldosterone	H02AA01
	Fludrocortisone	H02AA02
	Desoxycortone	H02AA03
	Betamethasone	H02AB01
	Dexamethasone	H02AB02
	Fluocortolone	H02AB03
	Methylprednisolone	H02AB04
	Paramethasone	H02AB05
	Prednisolone	H02AB06
	Prednisone	H02AB07
	Triamcinolone	H02AB08
	Hydrocortisone	H02AB09 (D07XA01 topical
		use)
	Cortisone	H02AB10
	Prednylidene	H02AB11
	Rimexolone	H02AB12
	Deflazacort	H02AB13
	Cloprednol	H02AB14
	Meprednisone	H02AB15
	Cortivazol	H02AB17
	Methylprednisolone, combinations	H02BX01
	Trilostane	H02CA01
	Phenylbutazone and corticosteroids	M01BA01
	Dipyrocetyl and corticosteroids	M01BA02
	Acetylsalicylic acid and corticosteroids	M01BA03
Methotrexate	Methotrexate	L04AX03
Statins	Atorvastatin	C10AA05
	Atorvastatin and acetylsalicylic acid	C10BX08
	Atorvastatin and amlodipine	C10BX03
	Atorvastatin and ezetimibe	C10BA05
	Atorvastatin and perindopril	C10BX15
	Atorvastatin, acetylsalicylic acid and perindopril	C10BX12
	Atorvastatin, acetylsalicylic acid and ramipril	C10BX06
	Atorvastatin, amlodipine and perindopril	C10BX11
	Cerivastatin	C10AA06
	Fluvastatin	C10AA04
	Gemigliptin and rosuvastatin	A10BH52
	Imipenem and cilastatin	J01DH51
	Lovastatin	C10AA02
	Lovastatin and nicotinic acid	C10BA01
	Nystatin	A07AA02, D01AA01, G01AA01
	Nystatin, combinations	G01AA51
	Pentostatin	L01XX08
	Pitavastatin	C10AA08
	Pravastatin	C10AA03
	Pravastatin and acetylsalicylic acid	C10BX02

PFIZER CONFIDENTIAL

Class of drug	Drug	ATC code
	Pravastatin and fenofibrate	C10BA03
	Rosuvastatin	C10AA07
	Rosuvastatin and acetylsalicylic acid	C10BX05
	Rosuvastatin and amlodipine	C10BX09
	Rosuvastatin and ezetimibe	C10BA06
	Rosuvastatin and valsartan	C10BX10
	Rosuvastatin, amlodipine and lisinopril	C10BX07
	Rosuvastatin, amlodipine and perindopril	C10BX14
	Rosuvastatin, perindopril and indapamide	C10BX13
	Simvastatin	C10AA01
	Simvastatin and acetylsalicylic acid	C10BX01
	Simvastatin and ezetimibe	C10BA02
	Simvastatin and fenofibrate	C10BA04
	Simvastatin, acetylsalicylic acid and ramipril	C10BX04
	Sitagliptin and simvastatin	A10BH51
Vaccinations	Anthrax antigen	J07AC01
	Brucella antigen	J07AD01
	Cholera, inactivated, whole cell	J07AE01
	Cholera, live attenuated	J07AE02
	Cholera, combinations with typhoid vaccine,	J07AE51
	inactivated, whole cell	
	Diphtheria toxoid	J07AF01
	Haemophilus influenzae B, purified antigen	J07AG01
	conjugated	
	Haemophilus influenzae B, combinations with	J07AG51
	toxoids	
	Haemophilus influenzae B, combinations with	J07AG52
	pertussis and toxoids	
	Haemophilus influenzae B, combinations with	J07AG53
	meningococcus C, conjugated	
	Meningococcus A, purified polysaccharides antigen	J07AH01
	Other meningococcal monovalent purified	J07AH02
	polysaccharides antigen	
	Meningococcus A,C, bivalent purified	J07AH03
	polysaccharides antigen	
	Meningococcus A,C,Y,W-135, tetravalent purified	J07AH04
	polysaccharides antigen	
	Other meningococcal polyvalent purified	J07AH05
	polysaccharides antigen	107.1770.6
	Meningococcus B, outer membrane vesicle vaccine	J07AH06
	Meningococcus C, purified polysaccharides antigen	J07AH07
	conjugated	107 4 1100
	Meningococcus A,C,Y,W-135, tetravalent purified	J07AH08
	polysaccharides antigen conjugated	107 + 1100
	Meningococcus B, multicomponent vaccine	J07AH09
	Meningococcus A, purified polysaccharides antigen	J07AH10
	conjugated	107 4 101
	Pertussis, inactivated, whole cell	J07AJ01
	Pertussis, purified antigen	J07AJ02

Class of drug	Drug	ATC code
J	Pertussis, inactivated, whole cell, combinations with	J07AJ51
	toxoids	
	Pertussis, purified antigen, combinations with toxoids	J07AJ52
	Plague, inactivated, whole cell	J07AK01
	Pneumococcus, purified polysaccharides antigen	J07AL01
	Pneumococcus, purified polysaccharides antigen	J07AL02
	conjugated	
	Pneumococcus purified polysaccharides antigen and	J07AL52
	haemophilus influenzae, conjugated	
	Tetanus toxoid	J07AM01
	Tetanus toxoid, combinations with diphtheria toxoid	J07AM51
	Tetanus toxoid, combinations with tetanus	J07AM52
	immunoglobulin	
	Tuberculosis, live attenuated	J07AN01
	Typhoid, oral, live attenuated	J07AP01
	Typhoid, inactivated, whole cell	J07AP02
	Typhoid, purified polysaccharide antigen	J07AP03
	Typhoid, combinations with paratyphi types	J07AP10
	Typhus exanthematicus, inactivated, whole cell	J07AR01
	Encephalitis, tick borne, inactivated, whole virus	J07BA01
	Encephalitis, Japanese, inactivated, whole virus	J07BA02
	Encephalitis, Japanese, live attenuated	J07BA03
	Influenza, inactivated, whole virus	J07BB01
	Influenza, inactivated, split virus or surface antigen	J07BB02
	Influenza, live attenuated	J07BB03
	Hepatitis B, purified antigen	J07BC01
	Hepatitis A, inactivated, whole virus	J07BC02
	Combinations	J07BC20
	Measles, live attenuated	J07BD01
	Measles, combinations with mumps, live attenuated	J07BD51
	Measles, combinations with mumps and rubella, live	J07BD52
	attenuated	3078632
	Measles, combinations with rubella, live attenuated	J07BD53
	Measles, combinations with mumps, rubella and	J07BD54
	varicella, live attenuated	0072231
	Mumps, live attenuated	J07BE01
	Poliomyelitis oral, monovalent, live attenuated	J07BF01
	Poliomyelitis oral, trivalent, live attenuated	J07BF02
	Poliomyelitis, trivalent, inactivated, whole virus	J07BF03
	Poliomyelitis oral, bivalent, live attenuated	J07BF04
	Rabies, inactivated, whole virus	J07BG01
	Rota virus, live attenuated	J07BH01
	Rota virus, pentavalent, live, reassorted	J07BH02
	Rubella, live attenuated	J07BJ01
	Rubella, combinations with mumps, live attenuated	J07BJ51
	Varicella, live attenuated	J07BK01
	Zoster, live attenuated	J07BK02
	Zoster, nive attenuated Zoster, purified antigen	J07BK03
	Yellow fever, live attenuated	J07BL01
	1 CHOW IEVEL, HVE ALLEHUALEU	JO/DEO1

Class of drug	Drug	ATC code
	Papillomavirus (human types 16 and 18)	J07BM02
	Papillomavirus (human types 6, 11, 16, 18, 31, 33,	J07BM03
	45, 52 and 58)	
	Smallpox, live attenuated	J07BX01
	Diphtheria-poliomyelitis-tetanus	J07CA01
	Diphtheria-pertussis-poliomyelitis-tetanus	J07CA02
	Diphtheria-rubella-tetanus	J07CA03
	Haemophilus influenzae B and poliomyelitis	J07CA04
	Diphtheria-hepatitis B-pertussis-tetanus	J07CA05
	Diphtheria-haemophilus influenzae B-pertussis-	J07CA06
	poliomyelitis-tetanus	
	Diphtheria-hepatitis B-tetanus	J07CA07
	Haemophilus influenzae B and hepatitis B	J07CA08
	Diphtheria-haemophilus influenzae B-pertussis-	J07CA09
	poliomyelitis-tetanus-hepatitis B	
	Typhoid-hepatitis A	J07CA10
	Diphtheria-haemophilus influenzae B-pertussis-	J07CA11
	tetanus-hepatitis B	
	Diphtheria-pertussis-poliomyelitis-tetanus-hepatitis B	J07CA12
	Diphtheria-haemophilus influenzae B-pertussis-	J07CA13
	tetanus-hepatitis B-meningococcus A + C	

Abbreviations: ATC = Anatomical Therapeutic Chemical.

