9.3. Variables

9.3.1. Variables and definitions

Table 3 summarises and defines the study variables to be collected and analysed in SNDS. Unless otherwise specified, these variables will be assessed during each patient's entire study period (baseline period and follow-up period).

This study will use code-based algorithms from the literature and/or other code lists to identify study variables. Published validated algorithms will be used where available.^{6, 7} All code-based algorithms and code lists will be reviewed and/or approved by Pfizer prior to

study initiation. Preliminary algorithms and/or codes are proposed in the following (Table 3); see also Annexes). Final algorithms and/or code lists may be refined as part of the statistical analysis plan (SAP) development. It is also to be noted that while laboratory tests performed are captured, results of laboratory tests are not available in the SNDS database.

Table 3. Operational definitions of study variables in Système National des Données de Santé

Variable	Role	Operational definition
Exposure		
Tofacitinib treatment	Exposure	Defined as having ≥1 ATC code (L04AA29) for a reimbursed prescription of tofacitinib during the indexing period. Index date is defined as the date of the first reimbursed prescription of tofacitinib.
Indication		
Indication	Indication (including off-label use)	Reported in the following categories: RA, PsA, UC and off-label/unknown based on hospital discharge diagnoses and active registration for diagnoses reported in the long-term disease (LTD) database for outpatients in the relevant time period. If there are no diagnosis codes for RA, PsA or UC, it will be categorised as off-label/unknown indications. Details will be further developed in the SAP.
		List of diagnoses codes for indications in ANNEX 13. LIST OF DIAGNOSIS CODES FOR INDICATIONS.
Primary Objective 1: I	Demographics, comorbi	dities and prior and current medications
		T OF CODES FOR COMORBIDITIES, unless otherwise
Age at tofacitinib initiation	Demographic	Calculated as the date of tofacitinib initiation minus the patient's month and year of birth and reported in the following categories: <18 years, 18-29 years and 30-39 years; 40-49 years; 50-59 years; 60-69 years; 70-79 years; ≥80 years; and <65 years and ≥65 years.
Sex	Demographic	Reported in the following categories: Male, Female and Unknown. Assessed on the date of the index tofacitinib prescription dispensing.

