Immunodeficiencies of interest	Comorbidity	Defined as ≥1 ICD-10 diagnosis code for immunodeficiency. Complete list in ANNEX 5. LIST OF DIAGNOSIS CODES FOR SELECT IMMUNODEFICIENCIES OF INTEREST.
Prior use of corticosteroids	Medication history	Defined as ≥1 prescription dispensing of a corticosteroid (as identified by ATC code[s]) in the 12 months prior to the index tofacitinib dispensing. Complete list in ANNEX 4. LIST OF ATC CODES FOR COMEDICATIONS OF INTEREST
Prior use of statins	Medication history	Defined as ≥1 prescription dispensing of a statin (as identified by ATC code[s]) in the 12 months prior to the index tofacitinib dispensing. Complete list in ANNEX 4. LIST OF ATC CODES FOR COMEDICATIONS OF INTEREST.

Table 3. Operational definitions of study variables in Système National des Données de Santé

Variable	Role	Operational definition
Prior use of any biologic	Medication history	Defined as ≥1 prescription dispensing of a biologic (as identified by ATC code[s]) in the 12 months prior to the index tofacitinib dispensing. Complete list in ANNEX 7. LIST OF ATC CODES FOR MEDICATIONS OF INTEREST TO AVOID WHILE TAKING TOFACITINIB.
Prior use of conventional synthetic DMARDs (csDMARDs)/ Immunomodulators	Medication history	Defined as ≥1 prescription dispensing of a csDMARD/ Immunomodulators (as identified by ATC code[s]) in the 12 months prior to the index tofacitinib dispensing. Complete list in ANNEX 7. LIST OF ATC CODES FOR MEDICATIONS OF INTEREST TO AVOID WHILE TAKING TOFACITINIB.
Prior use of MTX	Medication history	Defined as ≥1 prescription dispensing of MTX (as identified by ATC code L04AX03) in the 12 months prior to the index tofacitinib dispensing.
Prior use of anti-TB therapy	Medication history	Defined as ≥1 prescription dispensing of anti-TB therapy (as identified by ATC code[s]) in the 12 months prior to the index tofacitinib dispensing.
Prior vaccination	Medication history	Defined as ≥1 procedure code, ≥1 ICD-10 code and/or ≥1 reimbursed prescription (as identified by ATC code[s]) for a vaccination, overall and stratified by live and non-live vaccinations (if available) in the 12 months prior to the index tofacitinib dispensing. Complete list in ANNEX 4. LIST OF ATC CODES FOR COMEDICATIONS OF INTEREST.

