Concomitant use of a contraindicated potent immunosuppressants	Comedication	Defined as ≥30 overlapping days' supply of a tofacitinib prescription dispensing and a prescription dispensing for a contraindicated potent immunosuppressants (as identified by ATC code[s]) during the follow-up period. Days of supply in SNDS will be approximated by reimbursed package size and per recommended posology. Duration of tofacitinib therapy defined in Section 9.3.2.
Concomitant use of MTX	Comedication	Defined as ≥30 overlapping days' supply of a tofacitinib prescription dispensing and a prescription dispensing for MTX during the follow-up period.
Concomitant use of a corticosteroid	Comedication	Defined as ≥30 overlapping days' supply of a tofacitinib prescription dispensing and a prescription dispensing for a corticosteroid (as identified by ATC code[s]) during the follow-up period.
Concomitant use of anti-TB therapy	Comedication	Defined as ≥30 overlapping days' supply of a tofacitinib prescription dispensing and a prescription dispensing for anti-TB therapy (as identified by ATC code[s]) during the follow-up period.

Table 3. Operational definitions of study variables in Système National des Données de Santé

Variable	Role	Operational definition
Primary Objective 2: Pr	escribers' adherenc	e to the tofacitinib aRMMs
		per indication and duration of use
Duration of tofacitinib	Outcome:	Defined in Section 9.3.2. Assessed during the follow-up
therapy	Adherence to	period.
	recommended	
	posology	
ADD	Outcome:	Defined in Section 9.3.3. Assessed during the follow-up
	Adherence to	period.
	recommended	
	posology	
A patient with an	Outcome:	Among RA/PsA patients is defined as 0 ICD-10 diagnosis
ADD of >11 mg	Adherence to	code for UC during baseline or follow-up period and an
during any of the 8-	recommended	ADD of >11 mg during any of the 8-week intervals.
week intervals and no	posology	
evidence of a		
diagnosis for UC		
A patient with an	Outcome:	Among UC patients, is defined as ≥ 1 prescription dispensing
ADD of ≥15 mg in	Adherence to	for a biologic (as identified by ATC codes) prior to the index
Weeks 17-24, Weeks	recommended	tofacitinib dispensing and an ADD ≥15 mg in any of the
25-32, Weeks 33-40 or	posology	intervals: Weeks 17-24, Weeks 25-32, Weeks 33-40 or
Weeks 41-48 of		Weeks 41-48 of follow-up.
follow-up and with		Complete list of biologics in ANNEX 7. LIST OF ATC
evidence of a		CODES FOR MEDICATIONS OF INTEREST TO AVOID
diagnosis for UC but		WHILE TAKING TOFACITINIB

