1.3	-0.50	Small	107	321
1.3	-0.55	Small	88	264
1.2	-0.20	Small	566	1698
1.2	-0.25	Small	362	1086
1.2	-0.30	Small	252	756
1.2	-0.35	Small	185	555
1.2	-0.40	Small	142	426
1.2	-0.45	Small	112	336
1.2	-0.50	Small	91	273
1.1	-0.20	Small	475	1425
1.1	-0.25	Small	304	912
1.1	-0.30	Small	212	636
1.1	-0.35	Small	156	468
1.1	-0.40	Small	119	357
1.1	-0.45	Small	94	282
1.0	-0.15	Small	698	2094
1.0	-0.20	Small	393	1179
1.0	-0.25	Small	252	756
1.0	-0.30	Small	175	525
1.0	-0.35	Small	129	387
1.0	-0.40	Small	99	297

Table 6. Sample size for comparing changes in the mean number of risk factors per patient across reporting periods

Standard deviation for the mean number of risk factors per patient	Difference in the mean number of risk factors between any two reporting periods	Cohen's d effect size ^a	Number of patients needed per reporting period ^b	Total number of patients needed for the entire study period per indication group b, c
0.9	-0.15	Small	566	1698
0.9	-0.20	Small	318	954
0.9	-0.25	Small	204	612
0.9	-0.30	Small	142	426
0.9	-0.35	Small	104	312
0.9	-0.40	Small	80	240
0.8	-0.15	Small	447	1341
0.8	-0.20	Small	252	756
0.8	-0.25	Small	161	483
0.8	-0.30	Small	112	336
0.8	-0.35	Small	83	249
0.7	-0.15	Small	342	1026
0.7	-0.20	Small	193	579
0.7	-0.25	Small	124	372
0.7	-0.30	Small	86	258
0.6	-0.10	Small	566	1698
0.6	-0.15	Small	252	756
0.6	-0.20	Small	142	426
0.6	-0.25	Small	91	273
0.5	-0.10	Small	393	1179
0.5	-0.15	Small	175	525
0.5	-0.20	Small	99	297
0.4	-0.10	Small	252	756
0.4	-0.15	Small	112	336
0.3	-0.10	Small	142	426

- a. Reference:¹⁰
- b. Assuming equal sample size across reporting period
- c. Bolded rows indicate minimum sample size required per scenario of baseline variance

Through a preliminary assessment, the SNDS database holds records for approximately 4,000 RA or PsA patients and 1,000 UC patients who initiated tofacitinib between January 2018 (start of indexing period) and December 2020. It is projected that approximately 8,000

RA or PsA and 2,000 UC patients who initiate to facitinib will be captured through the end of the indexing period (e.g., December 2024).

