9.9.2. Missing data and/or incomplete data

The French SNDS database and linked datasets are claims and hospital practice datasets where missing data are possible. Missing and/or incomplete data mainly applies to causes of death, which is not a variable of interest in this study. The use of multiple linked data sources (primary care, hospital, pharmacy data and central death registrations) has the potential to reduce missing and/or complete data and improve exposure and/or outcome ascertainment. Data on treatments administered over-the-counter or in hospital are not available (excluding for medications invoiced in addition to the hospital disease-related group) nor laboratory results, as described above.

To avoid missing or the input of inaccurate data, quality control processes are performed prior to the data being integrated in the SNDS.³¹

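### The corticosteroid code list in Annex 4 contains no intestinally acting steroid although UC is an analysis group, and it leaves the status of trilostane and topical hydrocortisone unclear

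*Protocol*

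**What the plan says.** Two rows of Table 3 (Section 9.3.1) use corticosteroids.

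- Prior use: "Defined as ≥1 prescription dispensing of a corticosteroid (as identified by ATC code[s]) in the 12 months prior to the index tofacitinib dispensing". This row refers to Annex 4 for the complete list.
- Concomitant use: "Defined as ≥30 overlapping days' supply of a tofacitinib prescription dispensing and a prescription dispensing for a corticosteroid", during follow-up. This row says that ATC codes identify the drug but cites no annex.

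Neither row restricts the route of administration.

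The corticosteroid block of Annex 4 lists systemic products under H02, three M01BA combinations, and trilostane under H02CA01. Its hydrocortisone row reads "H02AB09 (D07XA01 topical" use, with the second code in brackets.

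The protocol marks its code lists as preliminary. Annex 4 opens with "All codes will be reviewed and updated prior to study initiation", and Section 9.3.1 adds "Final algorithms and/or code lists may be refined as part of the statistical analysis plan (SAP) development".

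**The concern.** Prior and current medication use belongs to Primary Objective 1 and is described by indication, with UC reported as its own group. Because Table 3 sets no route limit, a reader of the report will take the figure to mean any corticosteroid. The list behind it does not deliver that: a class of steroid that acts in the bowel is absent. Nor is it a clean systemic list, because it carries one dermatological code and one drug outside the corticosteroid groups.

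At stake is the accuracy of one descriptive figure, the share of UC initiators with prior steroid use and, if the same list is applied, with concomitant use. Two programmers could also code the bracketed D07XA01 entry differently from the same text.

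**Working it through.** No sample size or test is involved. The check is a count of the list, a search of the other annexes, and a comparison with Table 3.

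**Step 1. Count of Annex 4, corticosteroid block, by ATC group**

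| Group | Codes |
|---|---|
| H02AA | 3 |
| H02AB | 16 (01 to 15, and 17) |
| H02BX | 1 |
| H02CA (trilostane) | 1 |
| M01BA | 3 |
| D07XA (bracketed, beside hydrocortisone) | 1 |
| A07EA | 0 |

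H02 total: 3 + 16 + 1 + 1 = 21. All codes: 21 + 3 + 1 = 25. Rows: 24, because hydrocortisone carries two codes.

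**Step 2. Other annexes.** No annex contains an A07EA code or names budesonide or another intestinally acting steroid. Annex 7 does use the neighbouring intestinal codes A07EC01, A07EC03 and A07EC04 for other drugs, so this part of the classification is in use elsewhere in the protocol.

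**Step 3. Trilostane.** H02CA01 is the only H02C code in the block. The meanings of H02C (antiadrenal agents) and A07EA (intestinal corticosteroids) come from the ATC classification, which the protocol adopts as its coding system. The protocol itself does not state them. The statin block of the same annex lists nystatin, pentostatin, and imipenem with cilastatin, which suggests that entries were gathered by matching names.

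**Step 4. Comparison with Table 3.** Prior use requires one dispensing of a listed code. A UC patient whose only steroid in the 12 months was an intestinal product has no listed code and is scored as unexposed. The direction of the error in UC, an understatement, follows from the list alone.

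**Step 5. Size.** The documents give no rate of intestinal or topical steroid use. Let s be the share of UC initiators with an intestinal steroid and no listed steroid in the prior year. This is an assumption. N is about 2,000, the projected number of UC initiators in Section 9.5.

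Patients misclassified = s × N:

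- s = 0%: 0
- s = 5%: 0.05 × 2,000 = 100
- s = 10%: 0.10 × 2,000 = 200
- s = 20%: 0.20 × 2,000 = 400

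The understatement in percentage points equals s.

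**The case against.** The strongest reply is that the lists are declared provisional and the SAP may refine them. That is true, but a general promise of review does not identify this gap. The printed list, in version 4.0, gives the wrong count for the definition beside it.

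A second reply is that most listed codes are H02A or H02B, so a systemic-only variable may have been intended. That is a fair reading, and under it leaving out intestinal products would be no error. Table 3 does not say so, however, and the trilostane and D07XA01 entries do not fit it.

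Third, UC treatment here follows inadequate response, loss of response or intolerance to conventional therapy or a biologic (Section 7). Many such patients may also have had a systemic steroid, which would make s small. The documents neither support nor exclude this.

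Three stronger readings are tempting and not supported.

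- A reader might infer that skin creams inflate steroid use, especially in PsA, so that the error runs in opposite directions by indication. D07XA01 stands in brackets and may be only a note that separates the topical code. Even if counted, it is a single code, and Section 9.9.2 says "Data on treatments administered over-the-counter or in hospital are not available". No overstatement is shown.
- A reader might infer that Annex 4 formally governs concomitant use. That row cites no annex. Annex 4 is the only corticosteroid list in the protocol, so its use there is likely, but this is an inference. The difficulty of assigning days' supply to a cream arises only if that inference holds and D07XA01 is counted.
- A reader might infer that a comparison of RA/PsA with UC is spoiled. None is planned: analyses are run by indication group, and the formal comparisons in Section 9.7.2.4 and Section 9.7.2.5 are across reporting periods.

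**Conclusion.** The point holds as a minor code-list correction. Annex 4 omits intestinally acting corticosteroids, includes trilostane, and does not settle whether D07XA01 is counted. As Table 3 is worded, prior steroid use in UC can only be understated by the omission. By how much is unknown, and it could be close to zero; the 0 to 400 patients above are an illustration on an assumed share.

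Corticosteroid use is tabulated only. It is not a VTE, CV or malignancy risk factor in Table 3, is not among the incompatible medications, and enters no risk score, regression or sample size. No conclusion on adherence to the risk minimisation measures depends on it.

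**What to change.** Before the code lists are finalised:

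1. In Table 3, rename the existing variable systemic corticosteroid and limit it to H02A, H02B and M01BA.
2. In Annex 4, remove trilostane (H02CA01) and state that D07XA01 is not counted.
3. Add a separate descriptive row for intestinal corticosteroids (ATC group A07EA), covering prior use and use while on tofacitinib.
4. Cite Annex 4 in the concomitant-use row.

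The cost is a code-list edit and one extra table row. It is best done before the extraction criteria are passed on, because Section 9.4 limits the extraction to variables relevant to the study.
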